20. PHARMACODYNAMIC OUTCOMES

The PD analysis set will be used for PD analysis.

Observed values, change from baseline and relative change from baseline for circulating cytokines,

Document: \\ieedc-nas01a\biosdata\AnaptysBio\ANB020\CYA74393\Biostatistics\Documentation\SAP\Final2018-02-07
Author: [REDACTED] Version Number: Final 1.0
Version Date: 07Feb2018

Template No: CS_TP_BS016 Revision 4
Effective Date: 01Apr2016

Reference: CS_WI_BS005

STATISTICAL ANALYSIS PLAN

AnaptysBio Inc
PROTOCOL ANB020-003
Page 32 of 36

differential WBC counts (circulating leukocytes), and cytokine levels released from pathogenic T-cells (ex vivo whole blood peanut response assay) will be summarized with descriptive statistics including 95% CIs for the mean by nominal time point and treatment. Relative change from baseline is calculated as (actual-baseline)/baseline and will be reported as percentage.

Comparison between ANB020 and placebo will be performed using a repeated measures ANCOVA model on observed values with treatment, time point of measurement, and treatment by time point interaction as fixed effects, and baseline value as a covariate. An unstructured covariance matrix will be used. If the model fails to converge, then appropriate covariance matrix (e.g., compound symmetric) will be selected based on Akaike Information Criteria (AIC). All tests of treatment effects will be conducted at a 2-sided alpha level of 0.05 or with 2-sided 95% CIs. The following statistics will be presented:

- o Least-squares (LS) mean for treatment difference
- o Standard error of LS mean of difference
- o 95% CI for LS mean treatment difference
- o p-value for comparison of ANB020 versus placebo

Log or other transformation may be applied upon specific parameters as appropriate to meet the analysis assumptions.

A listing of PD blood sample collection date and times will be provided. A subject listing of all PD data (serum cytokines IL-4, IL-5, IL-9, IL-13, IL-33 and sST2, leukocytes in whole blood, and cytokine levels released from pathogenic T-cells following the ex vivo whole blood peanut response assay) will be provided. All PD parameters will be summarized as described in [Section 6](#), General Considerations, and observed values will be presented graphically in scatter plots of individual, mean, and median values by treatment and study day.

21. GENETIC ANALYSIS

Not applicable.

22. DATA NOT SUMMARIZED OR PRESENTED

The unscheduled visits will not be summarized, but listed.

Document: \\ieedc-nas01a\biosdata\AnaptysBio\ANB020\CYA74393\Biostatistics\Documentation\SAP\Final2018-02-07
Author: [REDACTED] Version Number: Final 1.0
Version Date: 07Feb2018

Template No: CS_TP_BS016 Revision 4
Effective Date: 01Apr2016

Reference: CS_WI_BS005

STATISTICAL ANALYSIS PLAN

AnaptysBio Inc
PROTOCOL ANB020-003
Page 33 of 36

APPENDIX 1. PARTIAL DATE CONVENTIONS

Imputed dates will NOT be presented in the listings.

Algorithm for Treatment Emergence of Adverse Events:

START DATE	STOP DATE	ACTION
Known	Known	If start date < study med start date, then not TEAE If start date >= study med start date, then TEAE
	Partial	If start date < study med start date, then not TEAE If start date >= study med start date, then TEAE
	Missing	If start date < study med start date, then not TEAE If start date >= study med start date, then TEAE
Partial, but known components show that it cannot be on or after study med start date	Known	Not TEAE
	Partial	Not TEAE
	Missing	Not TEAE

Document: \\ieedc-nas01a\biosdata\AnaptysBio\ANB020\CYA74393\Biostatistics\Documentation\SAP\Final2018-02-07
Author: [REDACTED] Version Number: Final 1.0
Version Date: 07Feb2018

Template No: CS_TP_BS016 Revision 4
Effective Date: 01Apr2016

Reference: CS_WI_BS005

STATISTICAL ANALYSIS PLAN

AnaptysBio Inc
PROTOCOL ANB020-003
Page 34 of 36

START DATE	STOP DATE	ACTION
Partial, could be on or after study med start date	Known	If stop date < study med start date, then not TEAE If stop date >= study med start date, then TEAE
	Partial	Impute stop date as latest possible date (i.e., last day of month if day unknown or 31st December if day and month are unknown), then: If stop date < study med start date, then not TEAE If stop date >= study med start date, then TEAE
	Missing	Assumed TEAE
Missing	Known	If stop date < study med start date, then not TEAE If stop date >= study med start date, then TEAE
	Partial	Impute stop date as latest possible date (i.e., last day of month if day unknown or 31st December if day and month are unknown), then: If stop date < study med start date, then not TEAE If stop date >= study med start date, then TEAE
	Missing	Assumed TEAE

Algorithm for Prior / Concomitant Medications:

START DATE	STOP DATE	ACTION

Document: \\ieedc-nas01a\biosdata\AnaptysBio\ANB020\CYA74393\Biostatistics\Documentation\SAP\Final2018-02-07
Author: [REDACTED] Version Number: Final 1.0
Version Date: 07Feb2018

Template No: CS_TP_BS016 Revision 4
Effective Date: 01Apr2016

Reference: CS_WI_BS005

STATISTICAL ANALYSIS PLAN

AnaptysBio Inc
PROTOCOL ANB020-003
Page 35 of 36

START DATE	STOP DATE	ACTION
Known	Known	If stop date < study med start date, assign as prior If stop date >= study med start date assign as concomitant
	Partial	Impute stop date as latest possible date (i.e., last day of month if day unknown or 31st December if day and month are unknown), then: If stop date < study med start date, assign as prior If stop date >= study med start date, assign as concomitant
	Missing	If stop date is missing, it could never be assumed a prior medication, assign as concomitant
Partial	Known	Impute start date as earliest possible date (i.e., first day of month if day unknown or 1st January if day and month are unknown), then: If stop date < study med start date, assign as prior If stop date >= study med start date, assign as concomitant

Document: \\ieedc-nas01a\biosdata\AnaptysBio\ANB020\CYA74393\Biostatistics\Documentation\SAP\Final2018-02-07
Author: [REDACTED] Version Number: Final 1.0
Version Date: 07Feb2018

Template No: CS_TP_BS016 Revision 4
Effective Date: 01Apr2016

Reference: CS_WI_BS005

STATISTICAL ANALYSIS PLAN

AnaptysBio Inc
PROTOCOL ANB020-003
Page 36 of 36

START DATE	STOP DATE	ACTION
	Partial	Impute start date as earliest possible date (i.e., first day of month if day unknown or 1st January if day and month are unknown) and impute stop date as latest possible date (i.e., last day of month if day unknown or 31st December if day and month are unknown), then: If stop date < study med start date, assign as prior If stop date \geq study med start date, assign as concomitant
	Missing	If stop date is missing, it could never be assumed a prior medication, assign as concomitant
Missing	Known	If stop date < study med start date, assign as prior If stop date \geq study med start date, assign as concomitant
	Partial	Impute stop date as latest possible date (i.e., last day of month if day unknown or 31st December if day and month are unknown), then: If stop date < study med start date, assign as prior If stop date \geq study med start date, assign as concomitant
	Missing	Assumed concomitant

Document: \\ieedc-nas01a\biosdata\AnaptysBio\ANB020\CYA74393\Biostatistics\Documentation\SAP\Final2018-02-07
Author: [REDACTED] Version Number: Final 1.0
Version Date: 07Feb2018

Template No: CS_TP_BS016 Revision 4
Effective Date: 01Apr2016

Reference: CS_WI_BS005

TABLE SHELLS

Placebo-Controlled Proof of Concept Study to Investigate ANB020 Activity in Adult Patients with Peanut Allergy

Study No. ANB020-003

Table Shells

AnaptysBio Inc.
PROTOCOL ANB020-003
Page 2 of 5

Output Templates Signature Page

Table Shells Draft 3.0 (Dated 07Feb2018) for Protocol ANB020-003.

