18.1. ADVERSE EVENTS

Adverse Events (AEs) will be coded using MedDRA Version 19.1.

Treatment emergent adverse events (TEAEs) are defined as AEs that started or worsened in severity on or after the date and time of the IP infusion or if the event represents an exacerbation of a condition observed pre-treatment. This excludes AEs due to BPCFC. AEs due to BPCFC during screening visit will be captured in medical history events.

Non treatment emergent adverse event (Non-TEAE) will be defined as any AE that started after the informed consent form has been signed and before the first dose of study medication and did not qualify for TEAE in terms of severity.

Adverse events with missing start dates will be considered treatment-emergent. AEs with missing stop dates or with stop dates after the end of the study date will be considered to have been ongoing at the end of the study.

The relationship to investigational product will be presented as "Related" versus "Not Related". Here the relationship categories "Unrelated" and "Unlikely" collected in the eCRF will be mapped to "Not Related", while the categories "Possible", "Probable" and "Unknown" will be mapped to "Related".

For each treatment, numbers of events, patients experiencing adverse events and percentage will be tabulated. The following summary tables will be provided by system organ class and preferred term for each treatment group:

- o number of patients with at least one TEAE
- o number of patients with at least one serious TEAE

Document: \\ieedc-nas01a\biosdata\AnaptysBio\ANB020\CYA74393\Biostatistics\Documentation\SAP\Final2018-02-07
Author: [REDACTED] Version Number: Final 1.0
Version Date: 07Feb2018

STATISTICAL ANALYSIS PLAN

AnaptysBio Inc
PROTOCOL ANB020-003
Page 26 of 36

- o number of patients with at least one TEAE by severity
- o number of patients with at least one TEAE by relationship to IP
- o number of patients with at least one TEAE leading to discontinuation from the study
- o number of patients with at least one TEAE leading to interruption of IP
- o number of patients with at least one TEAE leading to death
- o number of patients with non-TEAE
- o number of patients with AEs due BPCFC

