...									

Note: BPCFC=Blind Placebo-Controlled Food Challenge

Programming Note (not part of table): Sort by patient number, start date, start time

Document: \\ieedc-nas01a\biosdata\AnaptysBio\ANB020\CYA74393\Biostatistics\Documentation\SAP\Final\2018-02-07

Author: [REDACTED]

Version Number: Final 1.0

Version Date: 07Feb2018

Listing 16 2 6 2
Oral Food Challenge Symptom Scoring - Full Analysis Set

Patient No / Treatment	Age/ Gender	Visit	Time point	Date/ Time of Assessment	Skin Rash/ Pruritus/ Urticaria/ Angioedema (Grade)	Nasal Sneezing/ Itching/ Congestion/ Rhinorrhea/ Airway obstruction (Grade)	Chest Wheezing (Grade)	Abdomen Nausea/ Abdominal pain/ Emesis/ Diarhea (Grade)
XXX/XXX	32/ Male	Baseline	Prior to challenge 1	DDMMYYYY/ hh:mm	3/ 2/ 0/ 3f	3/ 2/ 0/ 1/ 3	3	3/ 2/ 0/ 3
		Day 14		-----				3/ 2/ 0/ 3
		Day 45		-----				3/ 2/ 0/ 3
XXX/XXX	31/ Female	---	Prior to challenge 2	DDMMYYYY/ hh:mm	3/ 2/ 0/ 3	3/ 2/ 0/ 1/ 3	0	3/ 2/ 0/ 3

XXX/XXX	28/ Female	----	After completion of challenge 2	DDMMYYYY/ hh:mm	3/ 2/ 0/ 3	3/ 2/ 0/ 1/ 3	3	3/ 2/ 0/ 3
...								

Programming Note (not part of table): Sort by patient number, start date, start time Continue for all other available visits

Document: \\ieedc-nas01a\biosdata\AnaptysBio\ANB020\CYA74393\Biostatistics\Documentation\SAP\Final\2018-02-07

Author: [REDACTED]

Version Number: Final 1.0

Version Date: 07Feb2018

Listing 16 2 7 1
Treatment Emergent Adverse Events - Safety Analysis Set

Patient No / Treatment	Age/ Gender/ Race	AE Number	System Organ Class/Preferred term/Verbatim Text	Start Date/ End Date	Did AE occur prior to the start of IP infusion?	AE Severity	Final Outcome	Action taken with the study drug	Relationship to study drug	Serious/ Criteria ^[1]	Did the AE cause the subject to discontinue from the study?	Was subject treated for AE?
XXX/XXX	32/ Male/ Race	xxxx	xx/xx/xx	DDMMYYY Y/ DDMMYYY Y	No	Severe	Recovered	Dose interrupted	Unlikely	Yes/ XXX	Yes	No
XXX/XXX	31/ Female/ Race	xxxx	xx/xx/xx	DDMMYYY Y/ DDMMYYY Y	Yes	Mild	Fatal	Drug permanently discontinued	Possible	Yes/ XXX	Yes	Yes
XXX/XXX	28/ Female/ Race	xxxx	xx/xx/xx	DDMMYYY Y/ DDMMYYY Y	Yes	Moderate	Lost to follow-up	Dose reduced	Probable	No	No	No
...												

Note:

[1] – If SAE led to death, then date of death and primary/ secondary cause of death are provided, if required hospitalization, then date of admission and date of discharge are provided

Programming Note (not part of table): Sort by patient number, AE number, start date

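### SAP 18.1 and SAP Appendix 1 give conflicting treatment-emergence rules for three kinds of adverse event, and nothing says which rule governs

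*SAP*

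**What the plan says.** SAP 18.1 gives the TEAE definition in words. It covers "AEs that started or worsened in severity on or after the date and time of the IP infusion", and also applies "if the event represents an exacerbation of a condition observed pre-treatment". Adverse events due to the food challenge are excluded. The companion definition of a non-TEAE is consistent with this: onset after consent and "before the first dose of study medication and did not qualify for TEAE in terms of severity". A separate sentence deals with missing onset: "Adverse events with missing start dates will be considered treatment-emergent".

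SAP Appendix 1 gives an algorithm for treatment emergence as a table of start-date and stop-date states. When the start date is known, the whole rule is "If start date < study med start date, then not TEAE" and "If start date >= study med start date, then TEAE", whatever the stop date. A partial start date that must fall before dosing gives not TEAE in every row. When the start date is missing and the stop date is known, or partial and imputed to its latest possible value, the rule is "If stop date < study med start date, then not TEAE"; otherwise the event is a TEAE.

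SAP 6.2 also bears on the dosing day: it treats adverse events that begin on the reference start date as post-baseline. Listing 16.2.7.1 carries the item "Did AE occur prior to the start of IP infusion", which the algorithm does not use.

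**The concern.** Safety and tolerability is a primary objective, and most adverse event tables in the SAP are built on the TEAE flag. If two sections of the same SAP set that flag differently, the counts depend on which one is programmed. The choice would then be made in code, or after results are known, and not in the plan.

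The affected kinds of event can occur here. Protocol 7.1.1.1 records adverse events from screening onward, and screening is 7 to 21 days before Day 1, so an event can be ongoing at dosing. Protocol 6.0 places Day 1 assessments before the infusion unless otherwise noted, so a complaint can be recorded that morning before any drug is given. Protocol 9.4.1 assigns the maximum intensity when an event changes in intensity. No text requires a worsening to be entered as a new record with a new start date.

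**Working it through.** The plan states no figure on this point. The check applies both rules to the same timing patterns. The inputs are the SAP 18.1 definition and missing-start sentence, the Appendix 1 rows, and the planned arm sizes (15 ANB020, 5 placebo, Protocol 6.2.2). Challenge-related events are left out.

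| Event pattern | SAP 18.1 | Appendix 1 | Agree? |
|---|---|---|---|
| Starts before dose date, no worsening | non-TEAE | not TEAE | yes |
| Starts before dose date, worsens after infusion | TEAE | not TEAE | **no** |
| Starts Day 1, before infusion, no worsening | non-TEAE | TEAE | **no** |
| Starts Day 1, after infusion | TEAE | TEAE | yes |
| Starts on a later day | TEAE | TEAE | yes |
| Start missing, stop before dose date | TEAE | not TEAE | **no** |
| Start missing, stop on or after dose date | TEAE | TEAE | yes |
| Start and stop both missing | TEAE | TEAE | yes |

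Three of the eight patterns conflict. That is a count of patterns and says nothing about how often each will occur. The worsening conflict also extends to partial start dates that must be pre-dose, because those rows have no worsening branch either.

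**Direction.** Relative to 18.1, Appendix 1 removes events in the worsening and missing-start patterns and adds events in the Day 1 pattern. The net effect cannot be signed in advance.

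**Where a worsened pre-dose event goes.** Under Appendix 1 it is counted in Table 14.3.1.7 (non-TEAEs by system organ class and preferred term) and in the non-TEAE lines of Table 14.3.1.1. It leaves the TEAE tables by severity (14.3.2.1) and relationship (14.3.3.1), the serious-TEAE table (14.3.1.3) and the TEAE listings. The listing shells cover TEAEs, subsets of TEAEs and challenge events; none covers non-TEAEs.

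**Effect of one patient.** Reclassifying one patient who has no other event in a given row moves that row by 100/n percentage points:

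- ANB020: 100/15 = 6.7
- Placebo: 100/5 = 20.0
- Overall: 100/20 = 5.0

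**The case against.** The best defence is that Appendix 1 is titled for partial dates and only supplements 18.1. SAP 6.1 refers to it after discussing partial or missing event dates, SAP 14 refers to it for partial medication dates, and 18.1 never cites it. It also lacks 18.1's exclusion of challenge-related events, so it cannot be the complete classifier. On that reading, 18.1 defines and Appendix 1 resolves dates. This is the sensible intent, and the fix adopts it. It does not remove the conflict, because the first row of the table handles fully known start and stop dates under a heading about treatment emergence, and no clause ranks the two sections.

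Four stronger readings might be inferred, and the documents do not support them.

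- *Appendix 1 is what would be programmed.* No text says so, and the missing challenge exclusion argues against using it alone.
- *Worsening events would be lost.* They would be in the wrong table and outside the detailed TEAE outputs, but still counted as non-TEAEs. Protocol 7.1.1.1 requires serious events after consent to be reported whatever this flag says.
- *Every event with a missing start date is affected.* The rules differ only when the known or imputed stop date is before dosing.
- *Date-only handling of Day 1 is a slip confined to the appendix.* SAP 6.2 states the same convention in the body of the SAP, so correcting Appendix 1 alone would leave a conflict with 6.2.

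One practical objection also stands. The listing shell shows one severity per event and no date of severity change. If sites already enter a worsening as a new event, its new start date makes Appendix 1 classify it correctly. If they do not, a worsening branch may not be programmable from the existing fields. The eCRF is not among the documents, so this cannot be settled here.

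**Conclusion.** The conflict is real for three defined kinds of event: worsening of a pre-dose event, Day 1 onset before infusion, and a missing start date with a pre-dose stop date. It affects a primary safety output, and following either section as written departs from the other.

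The number of patients affected cannot be derived from the documents and may be small. Reactions to the screening food challenge go to medical history, which narrows the pool of pre-dose events, and the Day 1 window is only the time before infusion. Safety is descriptive, with no between-group comparison (SAP 18), so no test result depends on it. With planned arms of 15 and 5, however, a single reclassified patient is visible in an incidence row.

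This rests on two assumptions: that a worsening is not routinely entered as a new record, and that the pre-infusion item in the listing shell is collected in the eCRF. The second is a fair inference from the shell. If the first is wrong, the worsening conflict largely disappears and the other two remain.

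**What to change.** Before database lock, make the SAP state one rule.

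1. Say that 18.1 is the TEAE definition, including worsening and the exclusion of challenge-related events, and that Appendix 1 only resolves dates.
2. Add a worsening branch to the Appendix 1 rows with a pre-dose start, both known and partial. If the eCRF holds no date of severity change, instruct sites to enter a worsening after infusion as a new adverse event record with its own start date.
3. For events that start on the dose date, classify by the listing item on occurrence before the infusion: yes means not TEAE unless the event worsens afterwards. The listing shell shows adverse event dates without clock times, so this item is the practical way to apply 18.1. Amend SAP 6.2 to match.
4. For a missing start date, keep the Appendix 1 stop-date rule and limit the 18.1 sentence to events whose stop date is not before dosing.

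The cost is a few lines of SAP text and flag programming. Item 2 may also need a data-entry instruction and some site queries; the other items need no new data if the pre-infusion item is in the eCRF.

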Table 14.3.4.4 Laboratory Parameters – Safety Analysis Set	31
Table 14.3.4.5 Shifts from Baseline in Clinical Laboratory Results – Safety Analysis Set	32
Table 14.3.5.1 12-Lead ECG – Safety Analysis Set	33
Table 14.3.5.2 Overall ECG and QT Changes from Baseline – Safety Analysis Set	34
Table 14.3.6.1 Vital Signs – Safety Analysis Set	35
Table 14.3.7.1 Spirometry – Safety Analysis Set	36
Table 14.3.7.2 Asthma Assessment of Symptom Control – Safety Analysis Set	37
Table 14.3.8.1 Physical Examination – Safety Analysis Set	38
Table 14.4.1.1 Summary of Serum Concentration of ANB020 – Pharmacokinetic Analysis Set	39
Table 14.4.1.2 Summary of Pharmacokinetic Parameters of ANB020 – Pharmacokinetic Analysis Set	40
Table 14.5.1.1 Summary of Pharmacodynamic Endpoints – Pharmacodynamic Analysis Set	41
Table 14.5.1.2 Statistical Analysis of Pharmacodynamic Endpoints – Pharmacodynamic Analysis Set	42

Table Shells

AnaptysBio Inc.
PROTOCOL ANB020-003
Page 6 of 42

Table 14 1 1 1
Patient Disposition – All Patients Screened Set

Category	ANB020 (N=XX) n (%)	Placebo (N=XX) n (%)	Total (N=xx) n (%)
Patients in Randomized Analysis Set	xx	xx	xx
Patients Administered the Treatment	xx (xx x)	xx (xx x)	xx (xx x)
Patients in FAS Population	xx (xx x)	xx (xx x)	xx (xx x)
Patients in SAF Population	xx (xx x)	xx (xx x)	xx (xx x)
Patients in PK Analysis Set	xx (xx x)	xx (xx x)	xx (xx x)
Patients in PD Analysis Set	xx (xx x)	xx (xx x)	xx (xx x)
Patients who Completed the Study	xx (xx x)	xx (xx x)	xx (xx x)
Patients who Completed the Study till Day 14	xx (xx x)	xx (xx x)	xx (xx x)
Patients who Completed the Study till Day 45	xx (xx x)	xx (xx x)	xx (xx x)
Patients who Discontinued the Study	xx (xx x)	xx (xx x)	xx (xx x)
Reason for Discontinuation			
Adverse Event	xx (xx x)	xx (xx x)	xx (xx x)
Death	xx (xx x)	xx (xx x)	xx (xx x)
Lack of compliance of protocol	xx (xx x)	xx (xx x)	xx (xx x)
Other	xx (xx x)	xx (xx x)	xx (xx x)

Source: Listing 16 1 2 1, 16 1 2 2

Note:

- N is the number of patients within each treatment group in the Randomized Analysis Set
- Percentages are based on the number of randomized patients in the respective treatment arm (N)
- Percentage for reason for discontinuation is based on number of patients who discontinued the study

Programming Note (not part of table): Add missing row where necessary Percentage for reason for discontinuation shall be taken from discontinued patients

Document: \\ieedc-nas01a\biosdata\AnaptysBio\ANB020\CYA74393\Biostatistics\Documentation\SAP\Draft\2018-02-07
Author: [REDACTED]

Version Number: Draft 3.0
Version Date: 07Feb2018

Table Shells

AnaptysBio Inc.
PROTOCOL ANB020-003
Page 7 of 42

Table 14 1 2 1
Protocol Deviations – Randomized Analysis Set

Deviations/Violations	ANB020 (N=XX) n (%)	Placebo (N=XX) n (%)	Total (N=XX) n (%)
Patients with major protocol deviations	xx (xx x)	xx (xx x)	xx (xx x)
Patients with category 1 deviation	xx (xx x)	xx (xx x)	xx (xx x)
Patients with category 2 deviation	xx (xx x)	xx (xx x)	xx (xx x)

Source: Listing 16 1 11 1

Note:

- N is the number of patients within each treatment group in the Randomized Analysis Set
- Percentages are based on the number of randomized patients in the respective treatment arm (N)
- Patients with multiple protocol deviations within the same category are counted only once under that category

Document: \\ieedc-nas01a\biosdata\AnaptysBio\ANB020\CYA74393\Biostatistics\Documentation\SAP\Draft\2018-02-07
Author: [REDACTED]

Version Number: Draft 3.0
Version Date: 07Feb2018

Table Shells

AnaptysBio Inc.
PROTOCOL ANB020-003
Page 8 of 42

Table 14 1 3 1
Demographic Characteristics – Randomized Analysis Set

Characteristic	Statistics	ANB020 (N=XX)	Placebo (N=XX)	Total (N=XX)
Age (years)	n Mean (SD) Median Min, Max	xx xx x (xx xx) xx x xx, xx	xx xx x (xx xx) xx x xx, xx	xx xx x (xx xx) xx x xx, xx
Gender	n (%)			
Male		xx (xx x)	xx (xx x)	xx (xx x)
Female		xx (xx x)	xx (xx x)	xx (xx x)
Child Bearing Potential Females	n (%)			
Yes		xx (xx x)	xx (xx x)	xx (xx x)
No		xx (xx x)	xx (xx x)	xx (xx x)
If Not Child Bearing Potential, <Categories>	n (%)			
Race	n (%)			
<Categories>		xx (xx x)	xx (xx x)	xx (xx x)
Ethnicity	n (%)			
<Categories>		xx (xx x)	xx (xx x)	xx (xx x)
Weight (Kg)			
Height (m)			
BMI(kg/m ²)			

Source: Listing 16 1 1 1

Note:

- N is the number of patients within each treatment group in the Randomized Analysis Set. Percentages are based on the number of randomized patients in the respective treatment arm (N)

Programming Note (not part of table): Add missing row where applicable. Present descriptive statistics similar to age for weight, height and BMI (present n, mean, SD, min, max, median)

Document: \\ieedc-nas01a\biosdata\AnaptysBio\ANB020\CYA74393\Biostatistics\Documentation\SAP\Draft\2018-02-07
Author: [REDACTED]

Version Number: Draft 3.0
Version Date: 07Feb2018

Table Shells

AnaptysBio Inc.
PROTOCOL ANB020-003
Page 9 of 42

Table 14 1 3 2
Other Baseline Characteristics – Randomized Analysis Set

Characteristic	Statistics	ANB020 (N=XX)	Placebo (N=XX)	Total (N=XX)
Skin Prick Test and ImmunoCAP Testing				
Performed Within 8 Weeks of Screening?	n (%)			
Yes		xx (xx x)	xx (xx x)	xx (xx x)
No		xx (xx x)	xx (xx x)	xx (xx x)
Peanut Extract				
Done	n (%)	xx (xx x)	xx (xx x)	xx (xx x)
Longest Wheal Diameter (mm)	n	xx	xx	xx
	Mean (SD)	xx x (xx xx)	xx x (xx xx)	xx x (xx xx)
	Median	xx x	xx x	xx x
	Min, Max	xx, xx	xx, xx	xx, xx
Orthogonal Diameter at the Mid-Point of Longest Axis (mm)			
Not Done	n (%)	xx (xx x)	xx (xx x)	xx (xx x)
Positive Control				
Done	n (%)	xx (xx x)	xx (xx x)	xx (xx x)
Longest Wheal Diameter (mm)			
Orthogonal Diameter at the Mid-Point of Longest Axis (mm)			
Not Done	n (%)	xx (xx x)	xx (xx x)	xx (xx x)
Negative Control				
Done	n (%)	xx (xx x)	xx (xx x)	xx (xx x)
Longest Wheal Diameter (mm)			
Orthogonal Diameter at the Mid-Point of Longest Axis (mm)			

Document: \\ieedc-nas01a\biosdata\AnaptysBio\ANB020\CYA74393\Biostatistics\Documentation\SAP\Draft\2018-02-07
Author: [REDACTED]

Version Number: Draft 3.0
Version Date: 07Feb2018

Table Shells

AnaptysBio Inc.
PROTOCOL ANB020-003
Page 10 of 42

Table 14 1 3 2
Other Baseline Characteristics – Randomized Analysis Set

Characteristic	Statistics	ANB020 (N=XX)	Placebo (N=XX)	Total (N=XX)
Not Done	n (%)	xx (xx x)	xx (xx x)	xx (xx x)
Drugs of Abuse				
Sample Collected?	n (%)			
Yes		xx (xx x)	xx (xx x)	xx (xx x)
Positive		xx (xx x)	xx (xx x)	xx (xx x)
Negative		xx (xx x)	xx (xx x)	xx (xx x)
No		xx (xx x)	xx (xx x)	xx (xx x)

Source: Listing 16 1 6 1, 16 1 8 1

Note:

- N is the number of patients within each treatment group in the Randomized Analysis Set
- Percentages are based on the number of randomized patients in the respective treatment arm (N)

Programming Note (not part of table):

- Add missing row where applicable
- Longest Wheal Diameter (mm) and Orthogonal Diameter at the Mid-Point of Longest Axis (mm) will be summarized using n, mean, SD, min, max, median

Document: \\ieedc-nas01a\biosdata\AnaptysBio\ANB020\CYA74393\Biostatistics\Documentation\SAP\Draft\2018-02-07
Author: [REDACTED]

Version Number: Draft 3.0
Version Date: 07Feb2018

Table Shells

AnaptysBio Inc.
PROTOCOL ANB020-003
Page 11 of 42

Table 14 1 3 3
Baseline Disease Characteristics – Randomized Analysis Set

Characteristic	Statistics	ANB020 (N=XX)	Placebo (N=XX)	Total (N=XX)
Quantiferon Gold Test^[1]				
Blood Sample Collected?	n (%)			
Yes		xx (xx x)	xx (xx x)	xx (xx x)
Positive		xx (xx x)	xx (xx x)	xx (xx x)
Negative		xx (xx x)	xx (xx x)	xx (xx x)
No		xx (xx x)	xx (xx x)	xx (xx x)
Virology				
Blood Sample Collected?	n (%)			
Yes		xx (xx x)	xx (xx x)	xx (xx x)
No		xx (xx x)	xx (xx x)	xx (xx x)
If Yes,				
Hepatitis B Surface Antigen <Categories>	n (%)	xx (xx x)	xx (xx x)	xx (xx x)
Hepatitis C Antibody <Categories>	n (%)	xx (xx x)	xx (xx x)	xx (xx x)
HIV Antibody <Categories>	n (%)	xx (xx x)	xx (xx x)	xx (xx x)

Table Shells

AnaptysBio Inc.
PROTOCOL ANB020-003
Page 12 of 42

Table 14 1 3 3
Baseline Disease Characteristics – Randomized Analysis Set

Characteristic	Statistics	ANB020 (N=XX)	Placebo (N=XX)	Total (N=XX)
----------------	------------	------------------	-------------------	-----------------

Source: Listing 16 1 9 1, 16 1 10 1

Note:

- N is the number of patients within each treatment group in the Randomized Analysis Set
- Percentages are based on the number of randomized patients in the respective treatment arm (N)
- [1] – Test for Tuberculosis

Programming Note (not part of table): Add missing row where applicable. This table can be modified as per the data requirement.

Table Shells

AnaptysBio Inc.
PROTOCOL ANB020-003
Page 13 of 42

Table 14 1 3 4
Serum Pregnancy Test – Randomized Analysis Set

	Visit	Characteristic	Result	Statistics	ANB020 (N=XX)	Placebo (N=XX)	Total (N=XX)
Serum Pregnancy Test ^[1]	Baseline	Test Performed	Yes No	n (%)	xx (xx x) xx (xx x)	xx (xx x) xx (xx x)	xx (xx x) xx (xx x)
		Outcome	Positive Negative	n (%)	xx (xx x) xx (xx x)	xx (xx x) xx (xx x)	xx (xx x) xx (xx x)
	<Visits>	-----					

Source: Listing 16 1 5 1

Note:

- N is the number of female patients within each treatment group in the Randomized Analysis Set
- Percentages are based on the number of randomized female patients in respective treatment arm (N)
- [1] – Only for women of child bearing potential

Programming Note (not part of table): Add missing row where applicable. This table can be modified as per the data requirement.

Document: \\ieedc-nas01a\biosdata\AnaptysBio\ANB020\CYA74393\Biostatistics\Documentation\SAP\Draft\2018-02-07
Author: [REDACTED]

Version Number: Draft 3.0
Version Date: 07Feb2018

Table Shells

AnaptysBio Inc.
PROTOCOL ANB020-003
Page 14 of 42

Table 14 1 4 1
Medical History – Randomized Analysis Set

System Organ Class Preferred Term	ANB020 (N=XX) n (%)	Placebo (N=XX) n (%)	Total (N=XX) n (%)
System Organ Class 1			
Preferred Term1	xx (xx x)	xx (xx x)	xx (xx x)
Preferred Term2	xx (xx x)	xx (xx x)	xx (xx x)
-----	xx (xx x)	xx (xx x)	xx (xx x)
System Organ Class 2			
Preferred Term1	xx (xx x)	xx (xx x)	xx (xx x)
Preferred Term2	xx (xx x)	xx (xx x)	xx (xx x)
-----	xx (xx x)	xx (xx x)	xx (xx x)

Source: Listing 16 1 3 1

Note:

- N is the number of patients within each treatment group in the Randomized Analysis Set
- Patients experiencing multiple events within the same SOC or preferred term are counted only once under those categories
- Percentages are based on the number of randomized patients in the respective treatment arm (N)

Programming Note (not part of table): Number and percentage (%) of patients with Medical History, sorted by decreasing frequency of system organ class and preferred term in total column. Mention "Uncoded" if there are any terms which are not coded yet

Document: \\ieedc-nas01a\biosdata\AnaptysBio\ANB020\CYA74393\Biostatistics\Documentation\SAP\Draft\2018-02-07
Author: [REDACTED]

Version Number: Draft 3.0
Version Date: 07Feb2018

Table Shells

AnaptysBio Inc.
PROTOCOL ANB020-003
Page 15 of 42

Table 14 1 5 1
Prior Medications by ATC Level – Safety Analysis Set

ATC Level 1 ATC Level 3	ANB020 (N=XX) n (%)	Placebo (N=XX) n (%)	Total (N=XX) n (%)
Number of Patients with at least one Prior Medication	xx (xx x)	xx (xx x)	xx (xx x)
ATC Level 1 ATC Level 3 ATC Level 3	xx (xx x) xx (xx x) xx (xx x)	xx (xx x) xx (xx x) xx (xx x)	xx (xx x) xx (xx x) xx (xx x)
-----	-----	-----	-----
ATC Level 1 ATC Level 3 ATC Level 3	xx (xx x) xx (xx x) xx (xx x)	xx (xx x) xx (xx x) xx (xx x)	xx (xx x) xx (xx x) xx (xx x)
-----	-----	-----	-----

Source: Listing 16 1 12 1

Note:

- N is the number of patients within each treatment group under Safety Analysis Set
- Medications are coded using WHO Drug Dictionary Dec 2016
- Patients with multiple usage of the same medication within the same ATC level 3 term are counted only once
- Percentages are based on number of patients within each treatment group under Safety Analysis Set(N)
- Only the patients with prior medications are summarized

Programming Note (not part of table): Number and percentage (%) of patients with prior medications, sorted by descending order of frequency in total column Add "Uncoded" if any events are not coded yet

If ATC level is not present or received from the DM, present this table for only PT's

Programming Note (not part of table): Similar table will be generated as follows:

Table 14 1 6 1 Concomitant Medications by ATC Level – Safety Analysis Set

Tables 14.1.6.1 will be summarized only for patients having atleast one concomitant medication.

Document: \\ieedc-nas01a\\biosdata\\AnaptysBio\\ANB020\\CYA74393\\Biostatistics\\Documentation\\SAP\\Draft\\2018-02-07
Author: [REDACTED]

Version Number: Draft 3.0
Version Date: 07Feb2018

Table 14 1 7 1
Study Medication Exposure – Safety Analysis Set

Characteristic	Statistics	ANB020 (N=XX) n (%)	Placebo (N=XX) n (%)	Total (N=XX) n (%)
Total Volume Administered	n	xx	xx	xx
	Mean (SD)	xx x (xx xx)	xx x (xx xx)	xx x (xx xx)
	Median	xx x	xx x	xx x
	Min, Max	xx, xx	xx, xx	xx, xx

Source: Listing 16 1 13 1 Note:

- N is the number of patients within each treatment group under Safety Analysis Set
- Percentages are based on number of patients within each treatment group under Safety Analysis Set(N)
- IV = Intravenous

Table Shells

AnaptysBio Inc.
PROTOCOL ANB020-003
Page 17 of 42

Table 14 2 1 1
Cumulative Tolerated Peanut Dose (Unit) During BPCFC – Full Analysis Set

Visit	Statistics	ANB020 (N=XX)	Placebo (N=XX)
Baseline	n	xx	xx
	Mean (SD)	xx x (xx xx)	xx x (xx xx)
	Median	xx x	xx x
	Min, Max	xx, xx	xx, xx
Day 14	n	xx	xx
	Mean (SD)	xx x (xx xx)	xx x (xx xx)
	Median	xx x	xx x
	Min, Max	xx, xx	xx, xx
Change from Baseline to Day 14	n	xx	xx
	Mean (SD)	xx x (xx xx)	xx x (xx xx)
	Median	xx x	xx x
	Min, Max	xx, xx	xx, xx
Day 45	n	xx	xx
	Mean (SD)	xx x (xx xx)	xx x (xx xx)
	Median	xx x	xx x
	Min, Max	xx, xx	xx, xx
Change from Baseline to Day 45	n	xx	xx
	Mean (SD)	xx x (xx xx)	xx x (xx xx)
	Median	xx x	xx x
	Min, Max	xx, xx	xx, xx

Source: [Listing 16 2 1 1](#)

Note:

- N is the number of patients within each treatment group under Full Analysis Set
- Baseline is defined as the nearest non-missing value before first dose of study medication

Programming Note: Continue this table for all available visits and respective change from baseline

Document: \\ieedc-nas01a\\biosdata\\AnaptysBio\\ANB020\\CYA74393\\Biostatistics\\Documentation\\SAP\\Draft\\2018-02-07
Author: [REDACTED]

Version Number: Draft 3.0
Version Date: 07Feb2018

Table 14 2 1 2
Primary Efficacy: Change from Baseline in Total Cumulative Tolerated Peanut Dose (Unit) During BPCFC at Day 14 – Full Analysis Set

Treatment LSMEANS (SE)	Treatment Difference ANB020 vs Placebo (Standard Error)	95% CI for Difference	p-value
ANB020 xxxx xxx (xxxx xxx)	Placebo xxxx xxx (xxxx xxx)	xxx xx (xxx xxx)	(xxx xx, xxx xx) 0 xxx

Note:

- P-value is obtained using ANCOVA model with treatment as fixed effect and baseline value as covariate

Programming Note: Refer SAP for Model

Table 14 2 2 1
OFC Symptom Score – Full Analysis Set

Visit	Statistics	ANB020 (N=XX)	Placebo (N=XX)
Baseline (Prior to challenge 1)	n	xx	xx
	Mean (SD)	xx x (xx xx)	xx x (xx xx)
	Median	xx x	xx x
	Min, Max	xx, xx	xx, xx
Prior to challenge 2	----		
After completion of challenge 1	----		
After completion of challenge 2	----		
2 hours after the challenge completion	----		
Unscheduled time point	----		
 Day 14			
Prior to challenge 1	n	xx	xx
	Mean (SD)	xx x (xx xx)	xx x (xx xx)
	Median	xx x	xx x
	Min, Max	xx, xx	xx, xx
Change from Baseline to Prior to challenge 1 of Day 14	n	xx	xx
	Mean (SD)	xx x (xx xx)	xx x (xx xx)
	Median	xx x	xx x
	Min, Max	xx, xx	xx, xx
 Day 45			
Prior to challenge 1	n	xx	xx
	Mean (SD)	xx x (xx xx)	xx x (xx xx)
	Median	xx x	xx x

Document: \\ieedc-nas01a\biosdata\AnaptysBio\ANB020\CYA74393\Biostatistics\Documentation\SAP\Draft\2018-02-07
Author: [REDACTED]

Version Number: Draft 3.0
Version Date: 07Feb2018

Table 14 2 2 1
OFC Symptom Score – Full Analysis Set

Visit	Statistics	ANB020 (N=XX)	Placebo (N=XX)
	Min, Max	xx, xx	xx, xx
Change from Baseline to time point of Day 45	n	xx	xx
	Mean (SD)	xx x (xx xx)	xx x (xx xx)
	Median	xx x	xx x
	Min, Max	xx, xx	xx, xx

Source: Listing 16 2 2 1

Note:

- N is the number of patients within each treatment group under Full Analysis Set
- Baseline is defined as the nearest non-missing value before first dose of study medication

Programming Note: Continue this table for all available visits and respective change from baseline

Table 14.2.2.2
Secondary Efficacy: Change from Baseline in OFC Symptom Score at Day 14 – Full Analysis Set

	Treatment LSMEANS (SE)	Treatment Difference ANB020 vs Placebo (Standard Error)	95% CI for Difference	p-value
ANB020	Placebo	xxxx xxx (xxxx xxx)	xxx xx (xxx xxx)	(xxx xx, xxx xx)

Note:

- P-value is obtained using ANCOVA model with treatment as fixed effect and baseline value as covariate

Programming Note: Refer SAP for Model

Table 14 2 3 1
Change from Baseline in Total Cumulative Tolerated Peanut Dose (Unit) During BPCFC and OFC Symptom Score at Day 45 – Full Analysis Set

Endpoint	Treatment LSMEANS (SE)		Treatment Difference ANB020 vs 95% CI for Difference (Standard Error)	p-value
	ANB020	Placebo		
Total Cumulative Tolerated Peanut Dose During BPCFC	xxxx xxx (xxxx xxx)	xxxx xxx (xxxx xxx)	xxx xx (xxx xxx)	(xxx xx, xxx xx)
